If a patient has a significant health status change after the baseline visit, but before the scheduled surgery, the study team will evaluate the patient's current medical status and determine if the health status change will affect the baseline data. In the rare occasion that the study team determines the patient's baseline data will be affected, the patient will be asked to come back to the clinic for a second baseline visit. The patient will be compensated for this visit and all baseline procedures will be repeated. As this repeated baseline visit is for data integrity only, and not for safety purposes, if the patient refuses to come back in for the repeat baseline visit, they will not be removed from the study. The study team will document this as a minor protocol deviation and the patient will continue on the study as previously planned. .

Prior to the day of surgery, the patient will complete a standard of care IMPACT visit. (IMPACT: VAPHS preoperative clinic – Interdisciplinary Medical Perioperative Assessment Consultation and Treatment).

Day of Surgery

On the day of surgery, the patient will receive anesthesia/study drug. Research questionnaires will be completed pre- and post-surgical procedure. Please refer to Appendix 1 for additional details.

In-Hospital Post-op Days (1-5)

Post-op in hospital visits will occur while the patient is in the hospital.

Follow-up visits 1 and 2

These two visits will be done in conjunction with the patient's standard of care orthopedic post-op visits.

Study Procedures:

Study Questionnaires:

Short-Form McGill Pain Questionnaire (SF-MPQ) – version 2 (Specific Aim)

The SF-MPQ questionnaire will be used to measure the subject's knee or hip pain. The questionnaire consists of 15 different qualities of pain and related symptoms, in which the subject is asked to rate the intensity of each symptom on a scale (none, mild, moderate, or severe). The questionnaire also includes two additional items relating to the patient's current pain. This questionnaire takes 5-10 minutes to complete.

SF-8 Survey

The SF-8 Health Survey is a short 8-question survey designed to measure the patient's overall health at 24-hour intervals. It takes less than 3 minutes to complete (21).

Short-Form 36 Health Survey (SF-36)

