For patient-reported outcome of function, we will use the data generated by Western Ontario and McMaster Universities Osteoarthritis Index Physical Function Subscale (WOMAC-PF). The entire WOMAC instrument will be administered. This instrument was developed based on patient input and is the instrument of choice to assess outcome post-TKA and THA (20). The WOMAC-PF consists of 17 items related to physical function. Each item is scored on a 5-point Likert-type Scale with descriptors from 0-4 (none, mild, moderate, severe, and extreme difficulty). Scores of each item are summed for a maximum total score on the WOMAC-PF of 68. Higher scores indicate worse functional limitations. Reliability and validity of this instrument have been established (25-27). This will be given before surgery and at Follow-Up Visit 2 after surgery. Licensing rights to this questionnaire have been purchased by the study team for use in this research study.

Falls Questionnaire:

Throughout the study, the patients will be asked about their falls history. The information collected will include but is not limited to, how many falls the patient experienced in the past year (done at baseline), how many falls since the last assessment (in-hospital visits and Follow-Up Visit 2), questions regarding loss of balance, whether or not the patient is afraid of falling, and was medical treatment sought after any falls.

Clinical Assessments

None of the clinical assessments listed below are being done due to safety concerns, as such, if the physical therapist or treating physician feels that due to the patients' medical condition (such as a knee immobilizer), that some or all of the physical therapy tests cannot be completed at the specified protocol time points; the physical therapy testing will be considered optional for these patients and will be done at the discretion of the treating physician and physical therapist. If physical therapy testing is not completed due to the patient preparing for discharge and/or the patient has been discharged, this will not be considered a protocol deviation.

Gait Speed: Self-selected gait speed is measured in meters/second while subjects walk a 4 meter path located in the middle of a longer path of 9 meters to avoid acceleration or deceleration. Subjects are asked to walk at their regular pace, and time is measured with a stop watch. This test takes around 2 minutes.

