5.0 Statistical Analysis

5.1 Analysis Plan

Data will first be assessed for outliers (+/- 2 SD from the mean) and normality. Outliers will be corrected, if possible, or dropped from the analyses. Distribution, measures of central tendency, variability, and normality will be examined. Data transformations or non-parametric techniques will be applied as needed. We will delete observations with missing values. Spearman correlation coefficients will be computed to examine associations between nerve block drug treatments, replacement surgery

type (hip versus knee), and the outcome measures (SF-MPQ, SF-8, SF- 36, WOMAC, FIM, repeated chair stand test, Opioid Symptom Distress Scale, Defense and Veterans Pain Rating Scale and its Supplemental Questions) from all time points (1 day, 2 day, 3 day, 4 day, Follow-Up Visit 1, Follow-Up Visit 2). Associations between the outcomes across time points will also be examined with Pearson (SF-MPQ, SF-8, SF-36, WOMAC, repeated chair stand test, Opioid Symptom Distress Scale) and Spearman (FIM, Defense and Veterans Pain Rating Scale and its Supplemental Questions) correlation coefficients. We will test all hypotheses and aims by conducting longitudinal multi-level modeling. The level-one unit will be the repeated measures across time, the level-two unit will be the individual patient, and the level-three unit will be nerve block type and surgical site (knee versus hip) groupings (with additional analyses involving age and diabetes status, reflecting the randomization strata). This mixed model procedure will allow the assessment of outcome and exposure variables relationships while adjusting for covariates, and separate assessments of fixed and random effects (i.e., group and individual-level data) using highly correlated repeated measures data. Covariates included in modeling will be age, diabetes status, gender, weight, smoking status, initial health status (e.g., baseline SF-8 / SF-36 and WOMAC), and concurrent general health status (e.g., daily SF-8, subsequent SF-36, and WOMAC).

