The **primary hypothesis** of an improvement in pain (measured by the SF-MPQ- version 2) 24 hr after surgery during in-hospital recovery comparing plain local anesthetics versus ISOC MMPNA will be tested using a mixed model. This procedure will test for nerve block drug treatment and surgical site (hip versus knee) effects, as well as an interaction between them. Differences in pain levels will also be examined across the study's day-of surgery, 1, 2, 3, and 4 day, and Follow-Up Visit 1 and Follow-Up Visit 2 time points. The secondary aims of short- and long-term physical therapy and rehabilitation-related benefits will also be examined for nerve block drug treatment and surgical site by a mixed model. The tertiary aim to determine differences in opioid-related side effects will use a mixed model. As with other analyses, there will be an examination for nerve block drug treatment and surgical site effects, as well as an interaction between them, along with analyses of the other randomization strata (age, diabetes) as described above.

The **exploratory aims** of physical therapy progress, return-to-home benefits, etc. will be examined using a mixed model. This procedure will test for nerve block type and surgical site effects, as well as an interaction between them. Number of days from the joint replacement procedure to the patient's home discharge will be assessed. Pain responses, as measured by the SF-MPQ – version 2, and use of postoperative opioids with additional measurement by the Opioid-Related Symptom Distress Scale will also be assessed. General health status will be evaluated with the SF-8 and SF-36. Measures of pain, analgesic side-effects, and general health status will be covariates included in the modeling of the effect of MMPNA on return-to-home.

Only after all data are analyzed and results are checked and verified by the biostatisticians will the study be unblinded.

5.2 Adverse Events. For adverse events, we will calculate cumulative probability using survival analysis techniques such as the product-limit estimator. Unlike proportions, product-limit estimators can be applied at various times following randomization, and can take into account when adverse events occur. The six-week incidence (and 95% CI) of individual adverse events by organ system and relatedness to the study will be calculated for each group. We will estimate the incidence of adverse

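### Deleting incomplete observations while adjusting for concurrent SF-8, SF-36 and WOMAC loses postoperative pain rows and randomised patients, and adjusts for variables measured after randomisation

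*Combined protocol and SAP*

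**What the plan says.** Section 5.1 gives one missing-data rule: "We will delete observations with missing values". It does not say whether an observation is a visit, a variable or a patient, or whether an instrument not scheduled at a visit counts as missing. The model description suggests a visit-row: "The level-one unit will be the repeated measures across time".

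The same section gives a single covariate list for the modelling. Five items are patient characteristics: weight, gender, smoking, diabetes and age. Health before surgery enters as "initial health status (e.g., baseline SF-8 / SF-36 and WOMAC"). The last item on the list is health status during follow-up, worded as "concurrent general health status (e.g., daily SF-8, subsequent SF-36, and WOMAC"). The primary hypothesis concerns SF-MPQ-2 pain "24 hr after surgery during in-hospital recovery comparing plain local anesthetics versus ISOC MMPNA will be tested using a mixed model". Section 5.1 also plans pain comparisons on the day of surgery, on Days 1 to 4 and at both follow-up visits.

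Section 4.3 describes SF-8 as "designed to measure the patient's overall health at 24-hour intervals" and SF-36 as a one-month measure. Of WOMAC it says "This will be given before surgery and at Follow-Up Visit 2 after surgery". The Appendix 1 calendar schedules the instruments accordingly.

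**The concern.** A row-wise deletion rule is harmless only if every covariate in the model exists on every row that matters. Here the three concurrent covariates are collected on different schedules, and the plan does not say which one enters at which visit. The rows and patients behind the treatment comparison therefore depend on a choice the analyst has to make.

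Three things are at stake:

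- Scheduled postoperative pain rows can drop out because a covariate was never due at that visit.
- A randomised patient with a recorded 24 h pain score can be excluded because one baseline item is blank.
- The concurrent measures are taken after the block has been given. If the block changes how patients rate their health, adjusting for that rating takes away part of the effect the trial is meant to estimate.

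**Working it through.** The documents give no count of analysable rows, so there is no stated figure to reproduce. The power figures in section 5.6 are for block duration and do not bear on this point.

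**Step 1. Schedule, from Appendix 1.**

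| | Post-procedure | Days 1–5 | Follow-Up 1 | Follow-Up 2 |
|---|---|---|---|---|
| SF-MPQ-2 | yes | yes | no | yes |
| SF-8 | no | yes | yes | no |
| SF-36 | no | no | no | yes |
| WOMAC | no | no | no | yes |

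Before surgery, SF-36 and WOMAC are taken at the Baseline Visit, and SF-8 first appears pre-procedure on the day of surgery. Postoperative SF-MPQ-2 rows: 1 (post-procedure) + 5 (Days 1–5) + 1 (Follow-Up 2) = 7. These are scheduled rows; a patient discharged early has fewer.

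**Step 2. Scheduled rows complete under each reading.**

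- A. SF-8, SF-36 and WOMAC all required in the same row: 0 of 7.
- B. The instrument scheduled at that visit (SF-8 in hospital, SF-36 and WOMAC at Follow-Up 2): 5 + 1 = 6 of 7. Day 1 is kept. The post-procedure row is lost because none of the three is due then.
- C. SF-8 as the only concurrent covariate: 5 of 7. Day 1 is kept. The post-procedure and Follow-Up 2 rows are lost.
- D. Daily SF-8, with the later SF-36 and WOMAC as one value per patient: Day 1 is kept only for patients who complete Follow-Up 2. At an assumed completion of 70% to 100%, that is 0.70 × 200 = 140 to 200 of 200 patients.
- E. Baseline covariates only: 7 of 7.

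**Step 3. Missing baseline covariates.** A baseline value is repeated on every row of a patient. If it is missing, every row is deleted, whichever reading applies. With independent missingness m on k covariates, the share of patients lost is 1 − (1 − m)^k. The documents give no rate, so m = 2% is an assumption.

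The list has eight baseline items. Age and diabetes status are on the Treatment Allocation Request form (section 4.2) and should be known for every randomised patient. That leaves k = 6 (gender, weight, smoking, SF-8, SF-36, WOMAC), or k = 3 if only the questionnaires are ever incomplete.

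- k = 3: 1 − 0.98³ = 0.059, about 12 of 200 patients and 2 of 40 controls.
- k = 6: 1 − 0.98⁶ = 0.114, about 23 of 200 patients and 5 of 40 controls.

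**Step 4. Timing of the concurrent measures.** The nerve blocks are given before surgery. Day 1 SF-8 and Follow-Up 2 SF-36 and WOMAC come afterwards. Section 4.3 lists bodily pain as one of the SF-36 sections, so that covariate overlaps with the outcome. The documents hold nothing from which to estimate how much of the treatment effect would be absorbed.

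**The case against.** The strongest reply is that the plan does not call for reading A. The concurrent measures are introduced as examples and qualified as daily and subsequent. The instruments' own intervals, such as SF-8 for "overall health at 24-hour intervals", point to a visit-appropriate choice. SF-8 and SF-MPQ-2 are both scheduled on Day 1, and the calendar footnote has both completed before that day's first physical therapy session. This stands. A reader might infer from the calendar that no postoperative row is usable, that 0 of 200 patients contribute, or that the 24 h outcome cannot be tested. The documents do not support that: it needs all three instruments to be mandatory in one row and unscheduled instruments to count as missing, and section 5.1 says neither.

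Two other tempting extensions also fail. One might put the baseline loss at 1 − 0.98⁸ = 15% by counting all eight covariates, but age and diabetes are needed to obtain the allocation. One might also say that the 4:1 group sizes would reveal the arms to whoever settles the covariate set. Section 4.2 uses five integer codes, four of them for the treatment arm, and the plan does not say when they are collapsed.

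It is also fair that section 4.4 plans point-of-entry checks against missing data, which may hold the rate below 2%, and that row-wise deletion lets a patient who misses one visit keep the others. Neither answers the loss of the post-procedure row, the exclusion of a patient for a blank baseline item, or adjustment for measures taken after randomisation.

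**Conclusion.** The concern holds in a limited form. The 24 h comparison can be run on the natural reading of section 5.1, but the stated rule and covariate list still do damage:

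- Depending on the reading, 6, 5 or 0 of the 7 scheduled postoperative SF-MPQ-2 rows survive. On the visit-appropriate reading the one lost is the only postoperative row on the day of surgery, a time point section 5.1 says it will examine.
- If the later SF-36 and WOMAC are patient-level covariates, the 24 h test is limited to patients who complete Follow-Up Visit 2.
- A missing baseline covariate drops a randomised patient who has the primary outcome, for about 6% to 11% of patients. That range rests wholly on the assumed 2% independent missingness over 3 to 6 covariates.
- Adjusting for concurrent health status can remove part of the treatment effect on pain. The mechanism follows from the timing; its size is unknown.

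The row counts follow from Appendix 1 and rest on deletion being by visit-row, which the multilevel structure suggests but the plan does not state.

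**What to change.** Change section 5.1 in three places.

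1. Remove concurrent SF-8, SF-36 and WOMAC from every model that estimates a treatment effect, and adjust for pre-randomisation covariates only. SF-8 has no Baseline Visit entry: its first value shares the pre-procedure column with study drug administration. If it is to serve as a baseline covariate, the plan should state that it is taken before allocation.
2. Replace the deletion sentence with wording such as: *Treatment effects are estimated by a likelihood-based mixed model using all observed postoperative outcomes. An instrument not scheduled at a visit is not a missing value.*
3. Add: *A patient with a missing baseline covariate stays in the analysis; the value is filled with the randomisation-stratum mean or, for a categorical item, a missing category.* This is one acceptable simple method among several. What matters is that it is fixed in advance and does not use the treatment arm.

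The cost is SAP wording only, with no new data or visits.

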ISOC MMPNA Block Group (n=80 TKA and 80 THA patients) will receive the ISOC 4-drug MMPNA nerve blocks at the L2-L4 and L4-S3 nerves/plexi. These blocks will be placed before the administration of spinal anesthesia, per our ISOC.

Active Control Block Group (n=20 TKA and 20 THA patients) will receive “active control” nerve blocks comprised of plain bupivacaine. As with the ISOC MMPNA Block Group, these blocks will be placed before the administration of spinal anesthesia, per our ISOC. Again, these blocks will involve the same L2-L4 and L4-S3 nerves/plexi as those for the ISOC MMPNA Block Group.

All study team members will be blinded to the nerve block treatment group/drug the patient receives/received for the described blocks. The only unblinded person regarding the study treatment will be the anesthesia team member who prepares the nerve block injection syringes, based on the randomization envelope assignment. This person who prepares the drug syringes will be otherwise uninvolved with the care of the study patient.

Table 1. Anatomic location of the analgesic nerve blocks used based on TKA versus THA

Basic description of regional anesthesia and analgesia care plan	TKA block details	THA details
Spinal anesthesia, L2-L4 and L4-S3 perineural/plexus single-injection nerve blocks	L2-L4 nerve block entails the femoral nerve in the groin. The L4-S3 nerve block entails the sciatic nerve as it emerges from the sciatic notch deep to the gluteal musculature.	L2-L4 plexus block entails the lumbar plexus within the psoas compartment, 2-3 inches lateral to the lumbar spine midline. The L4-S3 plexus block entails the lumbosacral trunk and parasacral plexus, which lies lateral to the lateral margin of the proximal sacrum. The plexus lies deep to the sacroiliac ligament.

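### Section 5.1 makes the treatment-by-site groupings the level-three unit of the model and also tests treatment, site and interaction on those same four cells, leaving fixed versus random unsettled

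*Combined protocol and SAP*

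**What the plan says.** Section 5.1 sets one model for the whole plan: "We will test all hypotheses and aims by conducting longitudinal multi-level modeling". It defines the hierarchy once. For the lower levels, "The level-one unit will be the repeated measures across time, the level-two unit will be the individual patient"; for the top, "the level-three unit will be nerve block type and surgical site (knee versus hip) groupings". Age and diabetes come in only as an addition: "with additional analyses involving age and diabetes status, reflecting the randomization strata".

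The next sentence says the mixed model allows "separate assessments of fixed and random effects (i.e., group and individual-level data", and a list of covariates follows.

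For the primary hypothesis (SF-MPQ-2 pain at 24 hr) Section 5.1 then states: "This procedure will test for nerve block drug treatment and surgical site (hip versus knee) effects, as well as an interaction between them". The same effects are to be examined for the other aims. The section does not say whether level three carries a random effect, and it names no method for the degrees of freedom.

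**The concern.** In a multilevel model, the unit at a given level is normally a member of a sampled population whose means vary around a common mean. Treatment arm is not of that kind here. Sections 4.1 and 4.2 randomise individual patients, with one envelope per subject within strata, so arm is a fixed contrast and the patient is the unit that carries its error. Knee versus hip is likewise a fixed, two-valued factor.

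Section 5.1 gives the same four cells two roles, as top-level units and as the effects under test. A programmer who coded the hierarchy literally would add a random intercept for the cells. Treatment could then be judged against between-cell variation, of which there is almost none to estimate from. A programmer who took the cells as fixed would get an ordinary patient-level test. The primary p-value should not depend on a choice left to the coding stage.

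**Working it through.** **Inputs.** Groupings: 2 block types x 2 sites = 4 (Section 5.1). Patients: "ISOC MMPNA Block Group (n=80 TKA and 80 THA patients" and "Active Control Block Group (n=20 TKA and 20 THA patients" (Section 4.1), so 160 + 40 = 200. Section 5.6 supplies a 15 hr difference (15 versus 30 hr), SDs of 7.5 and 15 hr, and a two-sided alpha of 0.05.

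**1. The plan's own figure.** The plan gives no df for the mixed model. The nearest figure is the power in Section 5.6, stated as 95% for 20 versus 80 patients per procedure.
- Pooled SD = sqrt[(19 x 7.5² + 79 x 15²)/98] = 13.87.
- SE = 13.87 x sqrt(1/20 + 1/80) = 3.467; noncentrality = 15/3.467 = 4.33.
- Power at 98 df = 99.0%, so the stated 95% is not reproduced. That is a separate matter. Section 5.6 is used here because it takes the patient as the unit and supplies an effect size.

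**2. Degrees of freedom, groups as fixed effects.**
- Whole trial: 200 - 4 (intercept, treatment, site, interaction) = 196 before covariates; critical t = 1.97.
- Within one procedure: 100 - 2 = 98; critical t = 1.98.

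**3. Degrees of freedom, groups as a random level with a between-cell (containment) rule.** Here df = number of level-three units minus fixed parameters that are constant within a unit.
- Treatment and site: 4 - 3 = 1; critical t = 12.71.
- With the planned interaction: 4 - 4 = 0; no test.
- Block type alone as the unit: 2 - 2 = 0.
- If age and diabetes also defined the cells (16 units): 16 - 5 = 11 with four main effects, or 16 - 6 = 10 with treatment-by-site added. Section 5.1 makes these additional analyses only.

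**4. What 1 df would cost.** These figures assume no true between-cell variance, which is the favourable case.
- Section 5.6 effect, 20 versus 80: 99.0% at 98 df against 27% at 1 df (25% to 31% across ways of combining the two SDs).
- Assumed standardised difference of 0.5 SD, 40 versus 160: SE = sqrt(1/40 + 1/160) = 0.177; noncentrality = 2.83; power 80% at 196 df and 18% at 1 df. Simulation gave 81% and 18%.

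**5. One illustrative fit.** One simulated dataset was used (one observation per patient, cells of 20, 20, 80 and 80, effect 0.8 SD, no true cell variance), fitted by REML with a random intercept for cell.
- With the interaction: treatment SE 1.37, against 0.26 at patient level. The fit reported a cell variance of 1.07 although none existed, because that variance is not identified.
- Main effects only: cell variance about zero, no convergence, and SE 0.18, the same as at patient level.

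**The case against.** The best defence is the sentence after the hierarchy. Read in order, its parenthesis pairs fixed with group and random with individual, which is the correct model. The language of testing treatment, site and interaction effects is also that of fixed effects, and Section 5.6 powers the trial on individual patients. All of this stands, and it favours the benign reading.

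A reader might infer something stronger: that the level-three sentence is the plan's only model specification, so the primary test is left with one or zero df. The documents do not support that. The specification continues in the next sentence and in the primary-hypothesis paragraph. Reaching 1 df needs both a random effect for the cells and a between-cell df rule, and the plan states neither. In the main-effects fit above, the standard error was unchanged, so any loss there would come only through the df rule. A model that fails to converge or returns an absurd standard error would also probably be noticed.

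The defence does not remove the problem. The parenthesis leaves the level-three definition in place, and nothing in the documents says which of the two statements governs.

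**Conclusion.** The point holds as a defect of specification with a conditional consequence. The stated hierarchy is wrong for an individually randomised trial, and its top level is fully aliased with the treatment, site and interaction effects the plan intends to test.

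If the groups are fixed, as the following sentence suggests, the treatment test has about 196 df before covariates (critical t 1.97) and only the wording is at fault. If level three is random and the df rule is between-cell, the test has 1 df (critical t 12.71) without the interaction. With it, there are 0 df and the cell variance is not identifiable. The power losses shown apply only to the 1 df case. They rest on the Section 5.6 duration inputs or on an assumed 0.5 SD effect, since the plan offers no SF-MPQ-2 variance.

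**What to change.** Delete the level-three unit and state in Section 5.1:

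*Two-level model, repeated measures (level 1) within patients (level 2). Nerve block type, surgical site and their interaction are fixed effects, with visit and treatment-by-visit, so that the primary test is the treatment contrast at 24 hr. Random effects or within-patient covariance are at patient level only. Degrees of freedom by Kenward-Roger or Satterthwaite.*

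Because the interaction is in the model, add whether the 24 hr contrast is averaged over the two procedures or reported within each.

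Keep the baseline covariates that Section 5.1 already lists (age, diabetes, gender, weight, smoking, initial health status); this point gives no reason to drop them. Do not mandate an unstructured covariance. Appendix 1 schedules SF-MPQ-2 at seven post-surgery assessments (post-procedure, days 1 to 5, Follow-Up Visit 2), which means 7 x 8/2 = 28 covariance parameters. Section 4.1 expects stays of 2 to 5 days, so the later in-hospital days will be sparse.

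The cost is SAP wording. No new data are needed, and the sample size does not change on this account.
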